8.12 Pregnancy Reporting

A female patient with a positive pregnancy test at Screening is ineligible for this study. If a female patient is found to be pregnant during the course of the study or during the first month after receiving the last dose of study drug, the Investigator should report the pregnancy to the CRO within 24 hours of being notified of the pregnancy. Details of the pregnancy will be recorded on the pregnancy reporting form. The patient should receive any necessary counseling regarding the risks of continuing the pregnancy and the possible effects on the fetus.

The pregnancy should be followed by the Investigator until completion. At the completion of the pregnancy, the Investigator will document the outcome of the pregnancy. If the outcome of the pregnancy meets the criteria for an SAE (i.e., postpartum complication, spontaneous abortion, stillbirth, neonatal death, or congenital anomaly), then the Investigator should follow the procedures for reporting an SAE outlined above.

Pregnancy occurring in the partner of a patient participating in the study should also be reported to the Investigator, who will then report this to the CRO and follow to outcome as described above.

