4.2 Inclusion Criteria

To be enrolled in the study, each patient must meet the following criteria at the Screening visit, except where specified:

1. Male or female of 18 to 85 years of age (inclusive);
2. Have a diagnosis of FAP with documented TTR mutation;
3. Have an NIS of 5 to 130 (inclusive) and a PND score of $\leq 3b$ (Note: This criterion must be met at the Screening/Baseline visit);
4. Have an NCS sum of the sural sensory nerve action potential (SNAP), tibial compound muscle action potential (CMAP), ulnar SNAP, ulnar CMAP, and peroneal CMAP of ≥ 2 points (Note: This criterion must be met at the Screening/Baseline visit);
5. Have a Karnofsky performance status of $\geq 60\%$;
6. Have an absolute neutrophil count (ANC) ≥ 1500 cells/mm³, and a platelet count $\geq 50,000$ cells/mm³;
7. Have aspartate transaminase (AST) and alanine transaminase (ALT) levels $\leq 2.5 \times$ the upper limit of normal (ULN), total bilirubin within normal limits, international normalized ratio (INR) ≤ 2.0 (patients on anticoagulant therapy with an INR of ≤ 3.5 will be allowed). Patients with total bilirubin $\leq 2 \times$ ULN are eligible if the elevation is secondary to documented Gilbert's syndrome (elevation of unconjugated bilirubin with normal conjugated bilirubin) and the patient has ALT and AST levels within normal ranges;
8. Have a serum creatinine $\leq 2 \times$ ULN;
9. No active infection with hepatitis B or hepatitis C by serology;
10. Women of child-bearing potential must have a negative pregnancy test, cannot be breastfeeding, and must be using 2 highly effective methods of contraception prior to screening, throughout study participation, and for 75 days after the last dose of study drug. Highly effective methods of birth control are defined in [Section 4.7](#);
11. Males with partners of child-bearing potential, must agree to use 1 barrier method (e.g., condom) and 1 additional method (e.g., spermicide) of contraception throughout study participation and for 75 days after the last dose of study drug; males must also abstain from sperm donation after the first dose of study drug through study participation and for 75 days after the last dose of study drug;

12. Must be willing and able to comply with protocol-required visit schedule and visit requirements and provide written informed consent.

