4.7 Pregnancy and Breastfeeding Restrictions / Contraception Requirements

Women of child-bearing potential must have a negative pregnancy test, cannot be breastfeeding, and must be using 2 highly effective methods of contraception prior to screening, throughout study participation, and for 75 days after the last dose of study drug. Highly effective methods of birth control result in a low failure rate (i.e., less than 1% per year)⁴³. Acceptable forms of effective contraception are defined as follows:

- Hormonal: established use of oral, implantable, injectable, or transdermal hormonal methods of conception;
- Placement of an intrauterine device (IUD);
- Placement of an intrauterine system (IUS);
- Mechanical/barrier method of contraception: condom or occlusive cap (diaphragm or cervical/vault cap) in conjunction with spermicide (foam, gel, film, cream or suppository);

Note: Failure rates indicate that, when used alone, the diaphragm and condom are not highly effective forms of contraception. Therefore the use of additional spermicides does confer additional theoretical contraceptive protection. However, spermicides alone are inefficient at preventing pregnancy when the whole ejaculate is spilled. Therefore, spermicides are not a barrier method of contraception and should not be used alone.

- Surgical sterilization of male partner (with the appropriate post-vasectomy documentation of the absence of sperm in the ejaculate; for female patients on the study, the vasectomized male partner should be the sole partner for that patient);

- Sexual true abstinence: when this is in line with the preferred and usual lifestyle of the patient. Periodic abstinence (e.g., calendar, ovulation, symptothermal, post-ovulation methods) and withdrawal are not acceptable methods of contraception.

Patients should be instructed to use two different forms of effective contraception from the list above. Examples of two forms of highly effective contraception are as follows:

- Oral, implantable, injectable, or transdermal contraceptives in conjunction with condom or diaphragm and spermicide;
- IUD in conjunction with condom or diaphragm and spermicide;
- Surgical sterilization of partner in conjunction with condom or diaphragm and spermicide.

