Males (including men who have had vasectomies) with partners of child-bearing potential, must agree to use 1 barrier method (e.g., condom) and 1 additional method (e.g., spermicidal foam, gel, film, cream, or suppository) of contraception throughout study participation and for 75 days (i.e., a whole spermatogenic cycle) after the last dose of study drug. Males must also abstain from sperm donation after the first dose of study drug through study participation and for 75 days after last dose of study drug.

Pregnancy reporting guidelines are provided in [Section 8.12](#).

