7.5.5.1 Pregnancy Test

The pregnancy test may be urine- or serum-based, at the discretion of the Investigator. The test will only be performed for women of child-bearing potential. The timing of the tests is specified in [Table 1-1](#), [Table 1-2](#), and [Table 1-3](#); additional testing may be done any time pregnancy is suspected. The results must be known prior to administration of

study drug. Patients who are pregnant are not eligible for study participation. Patients who become pregnant while on study will be followed until the pregnancy outcome is known (see [Section 8.12](#)).

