8.5 Adverse Event Reporting Period

AEs and SAEs will be reported according to the following timeframes:

- For patients who complete the study, AEs will be assessed through the End of Study visit on Day 567 or the Follow-up visit on Day 602 (depending whether or not the patient plans to roll over to the open-label extension study). All AEs that occur after the start of study drug administration on Day 0 must be reported in detail on the appropriate CRF page and followed to satisfactory resolution, or through the end of study visit on Day 567 or Day 602 (depending whether or not the patient plans to roll over to the open label extension study) after the last dose of study drug administration. SAEs will be followed through the end of study visit on Day 567 or Day 602 (depending whether or not the patient plans to roll over to the open label extension study), or until satisfactory resolution, or until the SAE is considered by the Investigator to be chronic or the patient is stable, whichever occurs first.
- For patients who meet the criteria for Rapid Disease Progression at Month 9 and receive their last dose of study drug on Day 252 but remain on the study, AEs will be followed through Day 294. Following Day 294, only study-procedure-related AEs will be collected (e.g., skin-biopsy-related AE, venipuncture-related AE). SAEs will be followed by the Investigator until satisfactory resolution or the Investigator deems the SAE to be chronic or stable.

- For patients who withdraw from the study early, ongoing AEs will be followed until resolution or 28 days from last dose, whichever occurs first. SAEs will be followed by the Investigator until satisfactory resolution or the Investigator deems the SAE to be chronic or stable.

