4.0	24 April 2014	
 The screening window was expanded from 28 days to 42 days to make it less restrictive for traveling patients. Corrected typographical errors identified in the SOA in version 3.0
5.0	04 August 2014	
 Inclusion Criterion #3 [Have an NIS of 5 to 100 (inclusive) (Note: This criterion must be met at the Screening/Baseline Visit)] changed to the upper limit NIS from 100 to 130 and added requirement for a Polyneuropathy Disability (PND) score of $\leq 3b$. Inclusion Criterion #7 [Have aspartate transaminase (AST) and alanine transaminase (ALT) levels $\leq 2.5 \times$ the upper limit of normal (ULN), total bilirubin within normal limits, albumin >3 g/dL (or >30 g/L), international normalized ratio (INR) ≤ 1.2 (patients on anticoagulant therapy with an INR of ≤ 3.5 will be allowed)] modified to remove albumin criterion and to increase INR criterion from ≤ 1.2 to ≤ 2.0 Inclusion Criterion #8 [Have a serum creatinine $\leq 1.5 \times$ ULN] modified from serum creatinine ≤ 1.5 to $\leq 2 \times$ ULN Inclusion Criterion #9 [Have negative serology for hepatitis B virus (HBV) and hepatitis C virus (HCV)] clarified to exclude only patients with an active hepatitis B or hepatitis C infection Inclusion Criterion #10 [Women of child-bearing potential must have a negative pregnancy test, cannot be breastfeeding, and must be using 2 highly effective methods of contraception prior to screening, throughout study participation, and for 1 month after last dose of study drug. Highly effective methods of birth control are defined in Section 4.7] modified to extend the period from 1 month to 75 days after last dose of study drug for WOCBP Inclusion Criterion #11 [Males with partners of child-bearing potential, must agree to use 1 barrier method (e.g., condom) and 1 additional method (e.g., spermicide) of contraception throughout study participation and for 1 month after the last dose of study drug; males must also abstain from sperm donation after the first dose of study drug through study participation and for 1 month after last dose of study drug] modified to extend the period that males with partners of child-bearing potential must use 1 barrier method and 1 additional method of contraception from 1 month to 75 days after the last dose of study drug Exclusion Criterion #1 [Has vitamin A levels consistent with vitamin A deficiency (<20 $\mu\text{g}/\text{dL}$)] removed Exclusion Criterion #16 [Has a known history of alcohol abuse or daily heavy alcohol consumption (females: more than 14 units of alcohol per week; males: more than 21 units of alcohol per week [unit: 1 glass of wine [125 mL] = 1 measure of spirits = $\frac{1}{2}$ pint of beer])] clarified to patients with a history of alcohol abuse within the past 2 years or daily heavy alcohol consumption Exclusion Criterion #17 [Participated in a clinical trial with antisense oligonucleotide, must have completed a 3-month wash-out prior to start of the study drug administration in this study] added to exclude patients who participated in a clinical trial with antisense oligonucleotide unless there is a 3 month wash-out period Exclusion Criterion #24 [Is under legal protection] modified to define "under legal protection" The protocol has been modified to permit select changes to the premedication regimen for an individual having difficulty tolerating the premedication regimen only after consultation with the study medical monitors. The sample size was modified to limit the number of patients with a Neuropathy Impairment Score (NIS) in the range of 101 to 130 to no more than 40 of the 200 planned patients to prevent overenrolling patients with more severe impairment.

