4.6.2. Adverse Events

All AEs will be coded using the MedDRA coding system (version 18.0 or later) and displayed in tables and data listings using SOC and preferred term.

Analyses of AEs will be performed for those events that are considered treatment-emergent, where treatment-emergent is defined as any AE with onset during or after the administration of study drug through 28 days following the last dose of study drug. In addition, any event that was present at baseline but worsened in intensity or was subsequently considered drug-related by the Investigator through the end of the study will be considered treatment-emergent. Events with a fully or partially missing onset date will be assumed to be treatment emergent unless it can be unequivocally determined (from the partial onset date and/or a partial or complete stop date) that the event occurred prior to the first administration of study drug.

Adverse events will be summarized by the numbers and percentages of patients reporting a given AE. A patient contributes only once to the count for a given AE (overall, by SOC, by preferred term). Overall event counts and frequencies may also be summarized.

An overall summary of AEs will include the number and percentage of patients with any AE, any AE assessed by the Investigator as related to treatment (definite or possible relationship), any severe AE, any severe AE related to treatment, any serious AE (SAE), any SAE related to treatment, any AE leading to treatment discontinuation, any study drug related AE leading to treatment discontinuation, any AE leading to study withdrawal, any study drug related AE leading to study withdrawal, and any deaths.

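### The duty to report a female patient's pregnancy (Protocol 8.12) can lapse before the 75-day contraception period ends

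*Protocol*

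**What the plan says.** Protocol 8.12 requires the investigator to report a pregnancy to the CRO within 24 hours of being notified, and to follow it to completion, when a woman taking part is "found to be pregnant during the course of the study or during the first month after receiving the last dose of study drug". A pregnancy in a male patient's partner is also reportable, with no end date stated.

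Inclusion criterion 10 (Section 4.2) requires women of child-bearing potential to use two highly effective contraceptive methods "throughout study participation, and for 75 days after the last dose of study drug". Section 4.7 repeats this and refers to 8.12 for reporting. The only reason given for the length of the period is in 4.7, for male patients: "for 75 days (i.e., a whole spermatogenic cycle) after the last dose of study drug".

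Section 7.5.5.1 adds: "Patients who become pregnant while on study will be followed until the pregnancy outcome is known". It points back to 8.12 and sets no longer window. The adverse event rules in 8.4 and 8.5 do not mention pregnancy.

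**The concern.** The sponsor asks women to avoid conception for 75 days after the last dose, but obliges the investigator to report a pregnancy only if it is found on study or within a month of that dose. A woman who has left the study and is found pregnant after that month, but still inside the precaution period, need not be reported or followed to outcome. The same applies to a woman who conceives early in the period, or even shortly before her last dose, if the pregnancy is recognised only after she has left and the month has passed. What is at stake is pregnancy-outcome information on a new agent, from the period the sponsor itself treats as needing precaution.

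**Working it through.** The plan gives no figure of its own to reproduce. The check compares the two windows in days.

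**Inputs**
- Reporting limit after the last dose: one month, taken as 30 days (8.12).
- Contraception period: 75 days (Inclusion criterion 10; 4.7).
- Last scheduled dose: Day 546. Final follow-up visit: Day 602 ±10 days, with a pregnancy test, only for patients not entering the extension (Table 1-2; 6.2.4.2).
- Contraceptive failure rate: less than 1% per year (4.7); 1% is used here as an upper figure.
- Conception to detection: 14 to 28 days (assumption; not in the documents).
- Number of women of child-bearing potential: not given, so results are per 100 women.

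**Gap by date of detection**
- Women who leave within about a month of the last dose: 75 − 30 = 45 days.
- Completers not entering the extension: participation runs to 602 − 546 = 56 days, so 75 − 56 = 19 days. With the visit window: 75 − 66 = 9 and 75 − 46 = 29 days.
- Women who stop drug but stay on study: no gap while they remain. A rapid progressor last dosed on Day 252 who stays to Day 567 is covered for 567 − 252 = 315 days.
- Extension entrants: governed by a protocol that was not supplied.

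The first group includes rapid progressors who withdraw at Day 273, 273 − 252 = 21 days after the last dose. They have no later visits (4.6), and the modified Day 273 visit lists no pregnancy test (6.4.1). Other early leavers are tested at the Early Withdrawal visit (6.3.1), but that covers only that date.

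**Gap by date of conception**

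A pregnancy detected by day *D* was conceived by about day *D* − lag, so the unreported span is 75 − (*D* − lag).
- Early leavers (*D* = 30): 75 − 16 = 59 days at lag 14; 75 − 2 = 73 days at lag 28.
- Completers (*D* = 56): 75 − 42 = 33 days at lag 14; 75 − 28 = 47 days at lag 28.

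**Expected pregnancies per 100 women** = 100 × rate × days / 365

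| Span (days) | At 1% per year |
|---|---|
| 45 | 0.123 |
| 19 (9 to 29) | 0.052 (0.025 to 0.079) |
| 59 to 73 | 0.16 to 0.20 |
| 33 to 47 | 0.09 to 0.13 |

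At an assumed 10% per year (poor adherence), 45 days gives 1.23 and 19 days gives 0.52. With 2:1 allocation, about one third of these women would have received placebo.

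**The case against.** The strongest reply is that this hardly matters. Two contraceptive methods are required, so 1% per year is already cautious, and the 10% figure is only an assumption. The women affected are those who leave early or decline the extension. That argument stands, and it sets the severity.

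A second reply is that the course of the study could mean the whole trial, so an early leaver stays covered while the trial runs. The wording allows this, but it would make the separate one-month limit largely redundant, so the patient-level reading is more natural. The ambiguity is itself a reason to clarify.

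Third, a congenital anomaly is a serious adverse event (8.2), and 8.11 requires all such events to be reported whatever their relation to study drug. This route is partial. Section 8.4 ties reporting to the periods in 8.5, normal outcomes would not be captured, and without a reportable pregnancy there is no duty to follow one to its outcome. A reader should therefore not infer that every adverse outcome in the gap escapes reporting, only that the plan has no reliable means of finding it.

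A reader might also infer that the one month is a missed update. The Amendment Summary says that in version 5.0 criterion 10 was "modified to extend the period from 1 month to 75 days after last dose of study drug for WOCBP". But one month is also close to the 28-day limits used elsewhere: for early withdrawals, "ongoing AEs will be followed until resolution or 28 days from last dose, whichever occurs first" (8.5), and in SAP 4.6.2 the treatment-emergent definition, "any AE with onset during or after the administration of study drug through 28 days following the last dose of study drug". The documents do not say which explains it, and the mismatch does not depend on the answer.

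**Conclusion.** The mismatch is real and sits in current text, but it is minor. By detection date, the duty lapses about 45 days before day 75 for early leavers and about 19 days (9 to 29) before for completers outside the extension. The spans of unreported conceptions, 59 to 73 and 33 to 47 days, rest on the assumed 14 to 28 day lag. Expected counts remain well below one per 100 women at the protocol's failure rate, and no efficacy result changes.

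Two stronger readings are not supported. The documents do not show that exposure between one month and 75 days harms a fetus. The only stated reason for 75 days concerns males, and the nonclinical summary is redacted. Section 1.3 reports that, after single doses in healthy volunteers, TTR returned to baseline by Day 70, but the protocol does not link this to the contraception period. Nor is the partner sentence in 8.12 shown to fall short, since it carries no end date.

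**What to change.** In 8.12, for female patients, keep the duty for pregnancies found during the study and replace the first-month limit with: *or is estimated to have conceived between the first dose and 75 days after the last dose of study drug, whenever detected*. Basing the limit on conception matters. A rule requiring detection by day 75 would still miss conceptions in the last 14 to 28 days of the period under the same assumed lag. Starting from the first dose keeps conceptions that precede the last dose but are found after exit.

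Align the sentence in 7.5.5.1 so that follow-up to outcome is not confined to pregnancies arising on study. Leave the partner sentence unchanged.

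The cost is a small notification duty, with no extra visits or tests. The change needs a protocol amendment with IRB/IEC and regulatory approval (10.2.3), so it is best included with other changes. Following a pregnancy after a woman has withdrawn consent may also need consent-form wording; the form was not available to check.

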9 STATISTICAL METHODS

9.1 Sample Size

Approximately 200 patients will be enrolled in this study. Of those 200 patients, no more than 40 patients will have a NIS range of 101 to 130. An mNIS+7 progression rate (primary endpoint) in the placebo group of 24 ± 16 points in 18 months was estimated using natural history data from FAP patients. A sample of 154 patients provides 90% power for a 2-sided test with an 8.95 point (37.5%) mean difference between treatment groups in the primary endpoint at 2-sided alpha = 0.05. Assuming a 25% random premature discontinuation rate (due to liver transplantation or other factors), the sample size for this study is approximately 200. Additional patients may be enrolled based on a recommendation to increase the sample size in the interim analysis.

9.2 Statistical Methodology

A full statistical analysis plan will be finalized prior to database lock.

9.2.1 Populations to be Analyzed

The following patient populations (i.e., analysis sets) may be evaluated and used for presentation of the data:

- Modified ITT (mITT) population: All patients who were randomized and received at least 1 dose of study drug;
- Per protocol (PP) population: All patients who completed the 18-month efficacy assessment visit and did not have any major protocol violations;
- Safety population: All patients who received at least 1 dose of study drug (analyzed as treated, not as randomized).

The primary population for efficacy analyses will be the mITT population; key efficacy results will also be analyzed secondarily for the PP population. For efficacy analyses, patients will be grouped according to the treatment to which they were randomized. The primary population for safety analysis will be the safety population. Patients will be grouped according to treatment received for summaries of safety.

